3.2 Primary Study Endpoints

The primary outcome variable is the difference in the individual slope of the MSNA – SaO₂ response curve at 6 weeks and baseline between treatment groups. Basal normoxic MSNA and MSNA responses during hypoxia will be compared between the three treatment groups. For purposes of quantification, MSNA is expressed as burst frequency (bursts/min), burst amplitude (arbitrary units) and total minute activity (burst frequency x mean burst amplitude). Total minute activity of mSNA is an effective way to capture the change in both burst frequency and burst amplitude. Both amplitude and burst frequency are influenced by disease states such as OSA and by environmental conditions such as hypoxia. Postganglionic mSNA in the right peroneal nerve will be recorded directly using the microneurography technique (95). The neural signals are passed to a differential preamplifier, an amplifier, a band-pass filter, and an integrator (time constant=100 ms). Placement of the recording electrode within a muscle nerve fascicle is confirmed by the presence of muscle twitches in response to electrical stimulation, the appearance of afferent activity in response to tapping or stretching of muscle, but not gentle stroking of skin, in the appropriate receptive fields, and other criteria. Once an acceptable neural recording (signal-to-noise ratio >3:1) is obtained, the subject is instructed to maintain the leg in a relaxed position for the duration of the study. Sympathetic bursts will be identified by computer-assisted inspection of the mean voltage neurogram.

3.3 Secondary Study Endpoints

Secondary outcome variables will include assessment measures of cerebral and forearm blood flow during basal conditions and during graded hypoxia before and after study drug treatment. Plasma catecholamine concentrations before and after study drug and change in plasma catecholamines during hypoxia will be assessed as a secondary indicator of sympathetic activation. Other secondary outcome variables will be assessed before and after study drug treatment, including: ventilation, aortic pulse wave velocity (a measurement of vascular stiffness), aortic augmentation index, % vasodilation during flow-mediated vasodilation (measurement of vascular endothelial function), apnea threshold, apnea-hypopnea index, % time spent below 90% oxygen saturation, heart rate variability, holter electrocardiogram measurements, and mean 24-

Version: 23, 7-25-17

hour blood pressure, mean nighttime blood pressure, mean daytime blood pressure, blood pressure load, and night/day blood pressure ratio.

4 Subject Selection and Withdrawal

4.1 Inclusion Criteria

Inclusion Criteria

- Males and females between ages of 21 and 65 years inclusive
- Apnea hypopnea index or respiratory disturbance index (RDI) greater than or equal to 25 events/hour (diagnosed by Polysomnography or home study)
- Subjects eligible for CPAP or BiPAP therapy. If subject is on CPAP or BiPAP, he/she must be on treatment for a minimum of 3 months prior to Visit 2.
- Hypertension by clinical history of high blood pressure readings or diagnosis of hypertension (may be controlled with non-exclusionary medications) or average blood pressure \geq 140/90 mm Hg (only require systolic OR diastolic to be above threshold, not both for inclusion). Blood pressures used for inclusion based on average blood pressure \geq 140/90 mm Hg will be (using two measurements in prior 12 months – in PHI or other records OR 1 prior elevated blood pressure and 1 blood pressure at screening)

4.2 Exclusion Criteria

Exclusion Criteria

- If subject not using CPAP, having AHI $>$ 60 events/hour or oxygen saturation \leq 65% during sleep
- Presence of clinical CV disease (coronary artery disease, angina, arrhythmias (subjects with sinus arrhythmias will be reviewed by PI for enrollment), stroke, TIA, cor pulmonale, etc.), heart failure, bruits, or diabetes mellitus by clinical diagnosis/history
- Presence of pulmonary disease that results in significant hypoxemia (resting SaO₂ $<$ 88%)
- Hypertriglyceridemia (triglycerides $>$ 300 mg/dL).
- Diabetes (fasting plasma glucose $>$ 125 mg/dL)
- Subjects taking angiotensin converting enzyme inhibitors, angiotensin receptor antagonists, renin inhibitors, potassium-sparing diuretics (without accompanying loop/thiazide diuretic), allopurinol, oxypurinol, febuxostat, amoxicillin, ampicillin, azathioprine or mercaptopurine. *(see below for examples)
- Subjects with chronic kidney disease (Serum creatinine $>$ 1.5 mg/dL) or history of significant hyperkalemia (Serum potassium $>$ 5.2 mEq/L) with ARB therapy
- Subjects with history of angioedema
- Subjects with bilateral, modified radical or radical mastectomies
- Subjects who have a Serum potassium $>$ 5.0 mEq/L at the screening visit
- Female subjects who are pregnant (determined by urine pregnancy test) or breastfeeding
- Subjects with active MRSA or VRE (vancomycin resistant enterococcus) infection
- History of adverse reaction to allopurinol, losartan, or zolpidem**
- Subjects who are currently receiving cancer treatment or have received cancer treatment in the past 1 year.
- Subjects who cannot swallow oral capsules
- Subjects who are hospitalized or who have been recently hospitalized (last 2 weeks)

Version: 23, 7-25-17

- Inability to comply with or complete the protocol or other reasons at the discretion of the investigators

*angiotensin converting enzyme inhibitors (lisinopril, enalapril, etc.)

Angiotensin receptor antagonists (losartan, valsartan, etc.)

Renin inhibitors (aliskiren)

Potassium sparing diuretics (spironolactone, eplerenone, triamterene without hydrochlorothiazide, etc.)

**If adverse reaction to zolpidem, may opt out of control of breathing study

4.3 Subject Recruitment and Screening

Screening Visit (Visit 1): Subjects will come to the CRU or their local recruitment site for a brief screening visit. **Subjects should be instructed to be fasting for at least 12 hours prior to their visit and patients should hold any blood pressure medications on the morning of VISIT 1 (they may take at end of VISIT or after).** Investigators will explain the study, answer questions, and complete the informed consent and HIPAA process. Potential subjects identified through sleep databases and registries will be contacted via telephone to obtain verbal consent or declination for participation in this study. A waiver of written documentation of informed consent has been approved by the IRB to obtain consent via telephone. At the in person screening visit, the subject will then sign a consent form witnessed by the study coordinator or investigator. The subject will then receive a signed copy of this consent form. All copies of the consent forms will be maintained in the subject's binder. The subject will then undergo:

- a history and physical with the CRU nurse practitioner
- undergo a 12-lead electrocardiogram (if the electrocardiogram has abnormalities of clear clinical significance, then a copy of the EKG with a letter explaining those abnormalities will be sent to the subject with instructions to share with his/her physician).
- take a urine pregnancy test (for females of child-bearing age),
- have a fasting blood sample taken to measure serum cholesterol, potassium, creatinine, uric acid, and glucose concentrations

If the subject declines participating in the study, any personal and health related information will not be retained and will be destroyed upon completion of the telephone call.

Subjects will not receive study medications until the end of Visit 3 and will be instructed to bring their study medication bottles with them to Visit 4 (two weeks after starting medication) and Visit 6 (6 weeks after starting medication). Study drug diary evaluation will be used to evaluate study drug adherence. Subjects will receive an auto-CPAP machine or CPAP compliance card to use during the study. Subjects will not receive payment for Visit 6 if they do not return the CPAP machine or CPAP compliance card. Subjects will be instructed to maintain the baseline CPAP use throughout the study. Subjects will complete baseline 24-hour ambulatory blood pressure monitoring (Visit 2) prior to receiving either study drug. This will take place prior to their overnight visit to Madison (Visit 3).

Study subjects will be recruited from the Wisconsin Sleep Center in Madison, Marshfield Clinic in the greater Marshfield, WI area, Aurora Bay Care in Green Bay, and Gundersen Health System in La Crosse, WI. Wisconsin Sleep initiated a research subject registry and database in August, 2008, and the subject registry invites all patients referred to clinic or laboratory to consider being contacted about research projects. Data that is maintained in the subject database includes patient name, date of birth, gender, contact information, sleep study data, and diagnoses. Drs. [name] and [name] will also recruit subjects at Wisconsin Sleep in their own clinics. Subjects will be recruited in clinics at Wisconsin Sleep and after their sleep study at Wisconsin Sleep or

Version: 23, 7-25-17

after a home study done by Wisconsin Sleep. Additional advertisements will be made available to subjects at other Sleep laboratories and clinics in the area, as well as at other clinics and medical centers in the greater Madison area (including, but not limited to: Baraboo sleep lab/clinic, Sauk prairie hospital sleep lab/clinic, St. Mary's sleep lab/clinic, Portage sleep lab/clinic, Reedsburg sleep lab/clinic, etc. Permission will be obtained prior to posting flyers or advertisements. An opt-out letter will be sent to qualifying subjects and the subjects will have 7 days to opt out before we will contact them to provide further information about the study and inquire as to their interest. Additional subjects who have participated in previous studies by investigators or other research groups who have expressed interest in future sleep apnea studies will be contacted about this study. Recruitment will also be completed with the use of social media and the internet. We will advertise on the UW Job Board, Craigslist, and Wisconsin Sleep's website. We will implement an email blast to the UW Madison students, faculty and staff as well as use campus and local newspapers and other media.

Recruitment at other sites:

We will also recruit from the sleep laboratories and sleep clinics at Marshfield Clinic, Marshfield, WI, Gundersen Health System, La Crosse, WI, and Aurora Bay Care, Green Bay, WI. Subjects will be recruited by the responsible investigators at the individual sites with the help of study coordinators. Subjects will be identified following sleep studies in the sleep laboratories and during visits to clinic. Subjects will be contacted and approached about study participation by individuals involved in his/her clinical care. Subjects may also be identified using advertisements in the community and at the local medical centers if necessary.

4.4 Early Withdrawal of Subjects

4.4.1 When and How to Withdraw Subjects

Allopurinol

If a subject experiences an adverse effect that is thought to be significant or serious (e.g. renal impairment, maculopapular rash, etc.) subjects' participation in the study will be ended.

Losartan

If a subject experiences clinically significant/serious adverse effects (angioedema, myalgias, acute renal failure), their participation will be ended. If the subject experiences increases in serum creatinine (> 0.5 mg/dL) or serum potassium (above 5.0 mEq/L) the subject's participation in the study will be ended. Blood pressure will also be measured at the two week monitoring visit (Visit 4). The dose of losartan will increase to 100mg daily if systolic blood pressure is > 120 mm Hg. For a systolic blood pressure between 100-120 mm Hg the subject may have dose increased if approved by study physician. If the subject's blood pressure is $< 100/60$ mm Hg and if the patient is dizzy and symptomatic during the study, the subject will discontinue study medication and go off study. This can be done via a phone encounter or via an additional (unexpected) visit. It is possible the subject's participation will be terminated if the study physicians feel that is appropriate.

Subjects may also be withdrawn from the study if they are diagnosed with a new and significant medical problem (e.g. they are hospitalized for an acute illness or major medical condition). Subjects may also be withdrawn from the study if they consistently fail to adhere to the protocol requirements. Study physicians will communicate with subjects' regular physician about care plans upon their withdrawal from the study.

Version: 23, 7-25-17

Additional (Unexpected) Visit:

If a subject experiences an adverse event that requires them to be seen by study staff, they should be scheduled for a visit to their local center as soon as is feasible. The PIs should be notified immediately and the physician at the local site should see the subject during the visit. Depending on the complaint, the AE should be evaluated with appropriate objective measures (blood tests, blood pressure/heart rate measurements, etc.) and the case report forms for "Additional Visit" should be filled out (in subject binder). These forms include:

AE form
Vitals form
Additional visit form
AE log

The study physician will determine if the subject should be discharged from the study (if subject is discharged, then complete the "subject off study" form). If the subject is discharged from the study, then he/she should have the 30-day post study evaluation performed 30 days after their study discharge (see below).

4.4.2 Data Collection and Follow-up for Withdrawn Subjects

We do not expect mortality or significant morbidity from the study. However, all subjects will be instructed to contact investigators if any problems arise after study participation is discontinued. Investigators will contact subjects who are withdrawn from the study 30 days after study discontinuation and periodically thereafter per study physician discretion if necessary. Data will be obtained and kept from any follow-up communications.

5 Study Drug

5.1 Description

Allopurinol and losartan are both FDA approved medications. Losartan is FDA approved for the treatment of hypertension. Allopurinol is approved for the treatment of gout. Study medications will be over encapsulated with lactose and all subjects will receive placebo with their active study medication in a double dummy design. Zolpidem will also be given to subjects (upon discharge from the CRU at Visits 3 and 6) to help them sleep during the control of breathing studies.

5.2 Treatment Regimen

Losartan 50 mg daily for two weeks, then increased to 100mg daily for 4 weeks

OR

Allopurinol 300 mg daily for 6 weeks

OR

Placebo capsule daily for 6 weeks

All three medications will be taken orally (in capsules) by subjects. The treatment regimen is summarized in Table 1.

Table 1. Treatment Regimen

Version: 23, 7-25-17

Arm	Treatment	Administered as:			
		Active Losartan 50mg Capsule Bottle A	Active Losartan 100mg Capsule Bottle B	Placebo	Allopurinol 300mg Capsule
Group I	Losartan	1 capsule daily on Days 1-14	1 Capsule daily on Days 15-42	None	None
Group II	Allopurinol	None	None	None	1 Capsule Daily on Days 1-42
Group III	Placebo	None	None	1 Capsule Daily on Days 1-42	None

Losartan subjects will take capsules from Bottle A for days 1-14, and capsules from Bottle B for days 15-42. If the subject's systolic blood pressure is > 120 mm Hg, the subject will continue to take capsules daily from Bottle A (days 15-42). If SBP is between 100-120 mm Hg, the subject may switch to bottle B with physician approval.

Allopurinol and Placebo will also have Bottle A and B for each treatment and will contain identical drug in Bottle A and Bottle B. Subjects will transition from Bottle A to Bottle B after day 14 in the allopurinol and placebo group. This is done to maintain study blinding.

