3.1 General Design

The proposed project is a randomized, double-blind, placebo-controlled, parallel three-treatment arm phase II clinical evaluation of allopurinol, losartan, and placebo in hypertensive patients with severe OSA. The proposed trial is based on preliminary data suggesting that both of these available medications may reduce chemoreflex sensitivity and endothelial function in patients with OSA. Subject enrollment will be conducted on a rolling basis during the three year study period and subjects will be randomized (stratified by baseline CPAP adherence) to one of the three treatments. Randomization will be stratified based on three categories of baseline CPAP

Version: 23, 7-25-17

adherence: < 1 hr, 1 – 4 hrs, and > 4hrs of CPAP use on average per night. This will ensure balanced CPAP use between treatment arms. Allopurinol will be initiated at 300 mg daily and the dose will remain constant for the six-week study session. Losartan will be initiated at 50 mg daily and the dose will be increased to 100 mg after two weeks if systolic blood pressure is above 120 mm Hg and as long as serum creatinine and potassium do not significantly increase. Subjects with SBP between 120-100 mm Hg may increase to 100 mg if approved by physician. If the subject's serum creatinine (> 0.5 mg/dL) or serum potassium (above 5.0 mEq/L) significantly increase, or if the subject experiences a significant side effect from the medication (e.g. maculopapular rash) the subject will be discontinued from the study. If the subject does not tolerate the losartan dose increase to 100 mg, his/her dose will be reduced back to 50 mg by study staff at request of subject. If the subject tolerates the dose increase, the losartan dose will then remain unchanged from the second to sixth week of the study. Patients in the placebo group will receive placebo capsules daily for six weeks that are identical in appearance to the overencapsulated losartan and allopurinol.

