5.6.1 Pregnancy Testing and Birth Control

Women of child-bearing age are eligible subjects for this study. However, since study drugs are pregnancy rate "D" (losartan) and "C" allopurinol, female subjects will take a urine pregnancy test at Visit 1 to ensure they are not pregnant. A urine pregnancy test will be repeated at Visit 1A if the study visit occurs more than 90 days after Visit 1. Furthermore, a urine pregnancy test will also be given at Visit 3 prior to study drug dispensing. The Pregnancy and birth control case report form should be completed at Visit 1, Visit 1A (if applicable) and Visit 3. On this case report form the method of birth control used should be documented and subjects are instructed to keep their birth control consistent throughout the study. Methods of birth control that are acceptable while participating in this study include oral contraceptives, hormonal contraceptives, hormonal implants, contraceptive patches, NuvaRing, intrauterine device hormonal, intrauterine device non-hormonal, barrier method, spermicide, post-menopausal for greater than or equal to two (2) years, tubal ligation, bilateral oophorectomy, or hysterectomy, vasectomy, or abstinence. If a female is practicing abstinence, she should confirm this, including duration, and initial and date the case report form.

5.7 *Blinding of Study Drug*

Allopurinol and Losartan tablets will be over encapsulated and dispensed to subjects with a placebo using a double-dummy design. Both subjects and investigators will be blinded to study drug assignment. The PRC will have unblinding information should the need arise to unblind a subject's study drug assignment. To obtain unblinding information, please call the University of Wisconsin Pharmaceutical Research Center at [contact].

5.8 *Receiving, Storage, Dispensing and Return*

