5.8.2 Dispensing of Study Drug

The PRC performs all required study drug reconciliation and inventory procedures on a regular basis. PRC drug record logs record the movement of study drugs out of PRC storage and all medications are checked by a PRC pharmacist prior to dispensing to the subject and study staff. Amount of study drug on hand and dispensed is constantly tracked in PRC records. All study drugs will be dispensed by the PRC to subjects during Visit 3 in Madison. Subjects will receive all study drugs for the 6-week treatment period at Visit 3 and will receive instructions from investigators prior to starting therapy. Zolpidem (supplied by the PRC) will be given to subjects upon discharge from the CRU at VISITS 3 and 6 to be taken immediately before (9-10pm) the control of breathing study on night two.

6 Study Procedures

See Appendix 2

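### Section 5.2 reverses the week-2 losartan titration rule of Sections 3.1 and 4.4.1, and its bottle rule differs by arm

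*Combined protocol and SAP*

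**What the plan says.** The week-2 losartan rule appears in three places.

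- **Section 3.1:** "the dose will be increased to 100 mg after two weeks if systolic blood pressure is above 120 mm Hg", provided creatinine and potassium have not risen significantly. Between 100 and 120 mm Hg an increase needs a physician's approval. If 100 mg is not tolerated, "his/her dose will be reduced back to 50 mg by study staff at request of subject".
- **Section 4.4.1:** "The dose of losartan will increase to 100mg daily if systolic blood pressure is > 120 mm Hg", with the same approval rule at 100-120 mm Hg. The reading is taken at Visit 4.
- **Section 5.2:** "If the subject's systolic blood pressure is > 120 mm Hg, the subject will continue to take capsules daily from Bottle A (days 15-42"). It goes on: "If SBP is between 100-120 mm Hg, the subject may switch to bottle B with physician approval".

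Table 1 in Section 5.2 identifies the losartan bottles: A is 50 mg and B is 100 mg, one capsule a day. For the other two arms, Section 5.2 says "Subjects will transition from Bottle A to Bottle B after day 14 in the allopurinol and placebo group", with no blood pressure condition. Both of their bottles hold the same drug, and the stated purpose of the switch is blinding.

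Two other provisions bear on this. Section 5.8.2: "Subjects will receive all study drugs for the 6-week treatment period at Visit 3". Section 5.7: "Both subjects and investigators will be blinded to study drug assignment".

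**The concern.** The sentence in Section 5.2 turns the titration upside down: the subject whose pressure calls for more drug is held at the starting dose.

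The wording matters in practice because of who acts on it. Subjects already hold the full six-week supply when they come to Visit 4. That visit is run by the local coordinator or, in Madison, by unit nurses (Section 6.2). Staff who do not know the arm have to give the instruction in bottles, and in the supplied text only Section 5.2 states the rule in bottles. A site that follows it under-doses one of the two active arms. Section 1.3 describes 50-100 mg as effective, but the only plasma concentration it cites in support is for 100 mg.

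There is also a blinding question. The pressure condition and the step back to 50 mg are written for losartan only. A blinded site cannot carry out a losartan-only rule. If the rule were carried out as written, staying on Bottle A after day 14, or going back to it, would mark the subject as losartan.

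**Working it through.** **Step 1. The rules side by side, losartan arm, days 15-42.**

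| Week-2 systolic pressure | Section 3.1 | Section 4.4.1 | Section 5.2 sentence |
|---|---|---|---|
| Above 120 mm Hg | 100 mg, if creatinine and potassium allow | 100 mg | Bottle A = 50 mg |
| 100-120 mm Hg | 100 mg if physician approves | 100 mg if physician approves | Bottle B = 100 mg if physician approves |

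The sections agree in the lower band and conflict in the upper one.

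**Step 2. Which statement is wrong.** Sections 3.1 and 4.4.1 agree with each other. Within Section 5.2, the regimen line, Table 1 and the sentence immediately before the disputed one all give 100 mg from day 15. Five statements therefore point to 100 mg and one to 50 mg. The disputed sentence also makes no clinical sense beside the one that follows it, which allows an increase at lower pressure. It is the sentence to correct.

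**Step 3. Dose consequence for one affected subject.** Inputs: 50 mg and 100 mg capsules, one daily, for 42 days (Table 1), with the switch after day 14. Full adherence is assumed.

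- Disputed sentence: 50 mg × 42 days = 2100 mg.
- Sections 3.1 and 4.4.1: 50 mg × 14 days + 100 mg × 28 days = 700 + 2800 = 3500 mg.
- Ratio: 2100 / 3500 = 0.60. Shortfall: 3500 − 2100 = 1400 mg.
- Mean daily dose: 2100 / 42 = 50.0 mg against 3500 / 42 = 83.3 mg.
- Days at half the intended dose: 42 − 14 = 28 of 42.

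**Step 4. Bottle rule by arm, with the upper-band error corrected.**

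| Situation | Losartan | Allopurinol, placebo |
|---|---|---|
| Above 120 mm Hg | Bottle B | Bottle B |
| 100-120 mm Hg, approved | Bottle B | Bottle B |
| 100-120 mm Hg, not approved | Bottle A | Bottle B |
| Bottle B not tolerated | Back to 50 mg (Bottle A) | No step back stated |

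The last two rows still differ by arm, so correcting the inequality alone does not make the rule workable under blinding.

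**What cannot be computed.** The documents give neither the share of losartan subjects above 120 mm Hg at week 2 nor a dose-response for the MSNA slope. The effect on the primary comparison therefore cannot be sized.

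**The case against.** The strongest reply is that Section 5.2 contradicts itself, so calling 2100 mg the dose under Section 5.2 lets one sentence override three others. A site would see a visible conflict, and the intended rule can be recovered from the rest of the protocol. The self-contradiction is real, but the other three statements give the default schedule, and the disputed sentence reads as a specific exception triggered by blood pressure. A careful reader could well follow the exception. The extra conflict strengthens the case that the sentence is wrong.

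Second, 50 mg lies inside the protocol's own dose range and is already accepted for subjects who cannot tolerate 100 mg or are not approved to increase, and no effect on the results is shown. That stands, and none is claimed here.

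Third, the blinding risk needs someone to apply an arm-specific rule without knowing the arm. A site applying the pressure rule to everyone would reveal nothing, and Section 3.1 already extends the week-2 laboratory monitoring to all subjects for this reason. That limits the point to a conditional one. Nothing in the text shows that those scoring MSNA see which bottle is in use. Even so, Section 5.2 prescribes an unconditional switch in the other two arms, so a site treating everyone alike would have to depart from it.

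Finally, Appendices 1 and 2 and the pharmacy's blinding scheme are not in the supplied text and may carry a correct bottle instruction. That is possible, but it would not make the Section 5.2 sentence right.

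**Conclusion.** The concern holds. Section 5.2 contains an operative dosing instruction, in current text, that is the opposite of Sections 3.1 and 4.4.1 for losartan subjects above 120 mm Hg. It must be corrected: a site that obeys it misdoses, and a site that doses as intended departs from it. The size is known per affected subject, as shown above, assuming one capsule daily and full adherence. The number affected is unknown.

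The arm-specific bottle rule is a secondary defect. It cannot be carried out by blinded staff and would reveal losartan if it were. No bias in the primary outcome is asserted.

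**What to change.** Replace the Section 5.2 losartan paragraph and the unconditional switch for the other arms with one blinded instruction for every subject at Visit 4:

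- Systolic pressure above 120 mm Hg, with creatinine and potassium acceptable: change to Bottle B.
- Systolic pressure 100-120 mm Hg: change to Bottle B only if the study physician approves; otherwise stay on Bottle A.
- Bottle B not tolerated: return to Bottle A.

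Sections 3.1 and 4.4.1 should refer to this instruction so that the rule is stated once in bottle terms.

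The cost is a protocol correction and a site notice, with no new data or subjects. Bottles A and B already hold identical drug in the allopurinol and placebo arms, so applying the rule there changes nothing those subjects receive. Fill counts are not stated, so the pharmacy should confirm that Bottle A covers all 42 days in every arm.

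### Section 5.2 keeps losartan subjects with systolic pressure above 120 mm Hg on 50 mg from day 15, where sections 3.1 and 4.4.1 raise them to 100 mg

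*Combined protocol and SAP*

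**What the plan says.** Section 3.1 sets the titration for the losartan arm. Subjects start on 50 mg, and "the dose will be increased to 100 mg after two weeks if systolic blood pressure is above 120 mm Hg", provided creatinine and potassium have not risen significantly. For the band below, "Subjects with SBP between 120-100 mm Hg may increase to 100 mg if approved by physician". A subject who does not tolerate 100 mg goes back to 50 mg. Section 4.4.1 repeats the rule for Visit 4: an increase above 120 mm Hg, and an increase at 100 to 120 only if the study physician agrees.

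Section 5.2 gives the regimen by bottle. Table 1 labels Bottle A as losartan 50 mg and Bottle B as losartan 100 mg. Five statements in 5.2 bear on day 15 onwards:

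- The regimen line: "Losartan 50 mg daily for two weeks, then increased to 100mg daily for 4 weeks".
- Table 1, Bottle B column, losartan row: "1 Capsule daily on Days 15-42".
- The first sentence under the table: "Losartan subjects will take capsules from Bottle A for days 1-14, and capsules from Bottle B for days 15-42".
- The next sentence: if "systolic blood pressure is > 120 mm Hg, the subject will continue to take capsules daily from Bottle A (days 15-42").
- The one after that: "If SBP is between 100-120 mm Hg, the subject may switch to bottle B with physician approval".

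For the other two arms, whose Bottles A and B are identical in content, 5.2 states no pressure condition: "Subjects will transition from Bottle A to Bottle B after day 14 in the allopurinol and placebo group".

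**The concern.** The sentence about pressure above 120 mm Hg tells staff to do the opposite of 3.1 and 4.4.1. Read together with the sentence after it, it turns the titration upside down: a subject at 110 may reach 100 mg with approval, while a subject at 135 may not reach it at all.

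This is an operative dosing instruction. Under 5.7 subjects and investigators are blinded, so staff at Visit 4 act on bottles and not on milligrams, and 5.2 is the only section in the text reviewed that states the rule in bottles. Under 5.8.2 subjects receive all six weeks of drug at Visit 3, so the week-2 step depends wholly on what they are told. Under 6.2 Visit 4 is run at each recruiting site by the local coordinator, or by unit nurses in Madison. Sites that read different sections could give the same kind of subject different doses, and the losartan arm would then not be the regimen that the design section describes.

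**Working it through.** The protocol states no figure to reproduce here. The check sets the statements side by side and reads off the losartan dose for days 15 to 42.

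| Place | SBP above 120 | SBP 100 to 120 |
|---|---|---|
| 3.1 | 100 mg, laboratory values permitting | 100 mg only if a physician approves |
| 4.4.1 | 100 mg | 100 mg only if the study physician approves |
| 5.2, regimen line | 100 mg, no condition | 100 mg, no condition |
| 5.2, Table 1 | 100 mg (Bottle B), no condition | 100 mg (Bottle B), no condition |
| 5.2, first sentence under the table | Bottle B = 100 mg | Bottle B = 100 mg |
| 5.2, second sentence | **Bottle A = 50 mg** | not addressed |
| 5.2, third sentence | not addressed | Bottle B = 100 mg only with approval |

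**Above 120 mm Hg.** Five statements give 100 mg and one gives 50 mg. The odd one out contradicts both design sections and three other statements in its own section. Because 3.1 and 4.4.1 name exactly the same subjects, no reading reconciles it with them.

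**What was probably meant.** Two small repairs would restore agreement. Writing Bottle B for Bottle A gives the rule of 3.1 directly. Turning the sign round, so that subjects below 120 stay on Bottle A, leaves the default of Bottle B above 120 and makes the approval sentence an exception to staying on A. The documents do not say which was intended, but both put subjects above 120 on Bottle B.

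**Size for an affected subject.** Days 15 to 42 are 42 − 14 = 28 days. Over those days, and therefore at the week-6 measurement, the daily dose is 50 mg under the faulty sentence and 100 mg under 3.1 and 4.4.1.

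**At 100 to 120 mm Hg.** The regimen line, Table 1 and the first sentence under it omit the approval condition, but the third sentence states it, in line with 3.1 and 4.4.1. This is a gap in the summary, not a second contradiction of the same weight.

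**Across arms.** 5.2 makes the bottle conditional in the losartan arm and unconditional in the other two. Staff who do not know the arm cannot follow both rules. If someone did apply them by arm, an instruction to stay on Bottle A would point to losartan.

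**The case against.** The strongest reply is that this is one misplaced letter or sign. Sections 3.1 and 4.4.1 agree, most of 5.2 agrees with them, and the approval sentence makes sense only as a restriction beside an automatic switch above 120. Section 9.4 gives all investigators access to the Visit 4 data, and Appendices 1 and 2, which are not in the text reviewed, may carry a Visit 4 instruction. That reply stands as to intent. It does not make the sentence harmless, because a coordinator holding two bottles would look in the section that speaks of bottles.

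A reader might infer more than the documents support:

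- *That Table 1 overrides physician approval at 100 to 120.* The table is introduced as a summary, and the condition stands directly beneath it. A footnote is enough.
- *That the dose would be doubled below 100 mm Hg.* No sentence says so. Sections 3.1 and 4.4.1 allow an increase only when a stated condition is met, and none covers that range; 4.4.1 also takes symptomatic subjects with pressure below 100/60 off study. This is not a separate error.
- *That a given share of the arm would be underdosed.* The documents give no week-2 pressure distribution, and the number above 120 is not the number misdosed, which depends on which section each site follows.
- *That the drug effect would be lost.* Section 1.3 treats 50 to 100 mg as the intended range. It cites levels above 1000 ng/mL after 100 mg, against a plateau at 500 to 750 ng/mL, and no figure for 50 mg. Total milligrams over six weeks say little either: 1.3 puts steady state at 20 to 45 hours, so the dose in use at week 6 is what matters.

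**Conclusion.** The sentence is wrong as written and should be corrected. The error is certain from the text alone and rests on no assumption. Its size for an affected subject is 50 mg instead of 100 mg daily from day 15 to day 42, and it falls on the subjects whom the design sections single out for the higher dose.

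The effect on the trial is uncertain. It depends on how many subjects exceed 120 mm Hg at Visit 4 and on how many sites follow 5.2 literally, and the documents give neither. A drafting slip is the likely cause, and the intended rule can be inferred. That limits the seriousness, but staff should not have to choose between opposite dose instructions. The missing conditions in Table 1 and the regimen line are a secondary point of clarity.

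**What to change.** Replace the bottle sentences in 5.2 with one Visit 4 rule:

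- SBP above 120: switch to Bottle B, provided the creatinine and potassium limits of 3.1 and 4.4.1 are met.
- SBP 100 to 120: Bottle B only with study physician approval; otherwise stay on Bottle A.
- SBP below 100: no increase; 4.4.1 applies if the subject is symptomatic.
- If 100 mg is not tolerated: return to Bottle A, as 3.1 allows.

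Add these conditions as a footnote to Table 1 and to the regimen line. Apply the same bottle rule in all three arms in place of the unconditional switch for allopurinol and placebo, so that blinded staff can follow it. In those two arms both bottles hold the same drug, so no dose changes.

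The cost is a wording change and a memo to sites. No procedure is added, since pressure and the laboratory values are already measured at Visit 4. The one practical downside is supply: the Bottle A fill must be checked to cover days 15 to 42 in every arm. The documents give no capsule counts. In the losartan arm, 3.1 and 4.4.1 already leave some subjects on 50 mg after day 14, so part of that supply is needed in any case.
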